### **9.3. Appendix 3: Review and Categorization of Adverse Events of Special Interest**

#### **9.3.1. Semi-Automated Adverse Events of Special Interest Coding Process**

A programming process will be performed for the creation of AE flags and adjudication variables for assigning each AE to at least a specific AESI category using the current version of Benlysta Program Safety Analysis Plan (PSAP) term of interest (TOI) and the GSK Medical Dictionary for Regulatory Activities (MedDRA) dictionary in effect at the time of reporting. The automated categorization of the reported AE into AESIs will be based on the following Benlysta pre-specified custom MedDRA queries (CMQ) variables:

- Neoplasms, hematological (CQ02NAM)
- Neoplasms, skin (CQ03NAM)
- Non-melanoma skin cancer-NMSC (CQ03NMFL)
- Neoplasms, solid (CQ01NAM)
- Neoplasms, unspecified (CQ04NAM)
- Opportunistic Infections (CQ06NAM)
- Herpes Zoster (CQ07NAM)
- Pneumonia (CQ10NAM)
- Sepsis (CQ08NAM)
- Tuberculosis (CQ11NAM)
- Suicide/self-injury (SMQ01NAM)
- Depression (CQ09NAM)

Any AEs that cannot be automatically categorized into AESI by the automatic process will be flagged for manual review by the GSK Study Medical Monitor and GSK Safety Evaluation and Risk Management (SERM) physician to adjudicate. The manual review process is as described in Section 9.3.2. The working instruction provided by GSK showing details of the automated steps is available on request from the GSK SABLE Study Lead Programmer or Statistician.

### 9.3.2. Review and Categorization of Adverse Events of Special Interest

All reported AE terms will be reviewed at the subject level by GSK Medical Monitor. The review and categorization of AEs are used to flag AESIs. The reviewers will categorize each AE into one of the following AESI category.

- Malignancies (excluding non-melanoma skin cancer - NMSC)
- Opportunistic infections (see protocol Appendix 1)
- Other infections of interest (see protocol Appendix 1)
- NMSC
- Serious psychiatric events (see protocol Appendix 2)
- Serious infections

Cases of mortality (death) are reported as all the events captured as fatal SAEs in the eCRF. All other AESI types are assigned based on the review outcome described above. For summary and reporting purpose, the eCRF field for reporting SAE will be used to separate serious and non-serious Opportunistic Infections and Other Infections of Interest AESI.

In addition to review by the GSK Medical Monitor, an independent review and categorization will be performed by safety physician for concurrence with the initial review using the same data and following the same convention of the main review. Identified discrepancies will be discussed and reconciled between the GSK clinical representatives (Medical Monitor and study Clinical Science Lead or designee) and the SERM physician. The reconciled record of categorization will be utilized in study reporting.

The identification, classification and categorization of AESI is planned to occur at least annually prior to the clinical database cut-off date for the scheduled annual post-approval European Medicines Agency (EMA) submission. It is anticipated that since this is an ongoing study and in-stream query process, categorization may change from one report to another, as additional information becomes available on safety events.

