- Opportunistic infections and other infections of interest: Opportunistic infections are a subset of infections that are caused by organisms that usually do not cause disease in immunocompetent individuals but which may cause illness, or more severe illness, when the immune system is suppressed. Since there are no general guidelines for labeling pathogens as opportunistic without considering the host's immune condition, identification of opportunistic infections in this study is based on a list of pathogens which, when present, may indicate immune suppression in a patient. These pathogens and infections in general are not observed in immunocompetent individuals and will be considered opportunistic. Pathogens and infections considered to be opportunistic include but not limited to those listed in [Appendix 1](#). All potential opportunistic infections (and other infections of interest as noted in [Appendix 1](#)), irrespective of seriousness, will be collected.
- Non-melanoma skin cancer: NMSC is a malignant growth of the external surface or epithelial layer of the skin. NMSC most often originates from the external skin surface as a squamous cell carcinoma or a basal cell carcinoma.

- Selected serious psychiatric events: Selected serious psychiatric events suggestive of mood disorders and anxiety, as defined in [Appendix 2](#), will be collected.
- Serious infections: Serious infections, including serious opportunistic infections, are defined as those that result in death, are life-threatening; require inpatient hospitalization or prolongation of existing hospitalization; require treatment with intravenous antimicrobials (eg, antibiotics, antifungals, antivirals); result in persistent or significant disability/incapacity; or are, based upon appropriate medical judgment, important medical events that may not be immediately life-threatening or result in death or hospitalization but may jeopardize the patient or may require intervention to prevent one of the other outcomes listed above. All serious infections will be collected. See [Section 7.1](#) for the definition of serious adverse events (SAEs).

Effectiveness

- Organ damage: The SDI ([Appendix 5](#)) is designed to capture items of irreversible organ damage present for at least 6 months ([Gladman et al, 1996](#)) occurring in patients with SLE regardless of exact cause. It consists of 12 organ system scales each having subscales comprised of up to 6 components.

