
1. Incidence rate will be calculated for each exposure group as follows:
 $\text{Incidence Rate} = \frac{\sum \text{at risk subjects with at least one event}}{\sum \text{subject years at risk}} \times 100$ 
 
- Incidence rate is defined as the number of 'at-risk' subjects experiencing first event (i.e. number of new cases) during the specified follow-up period divided by total subject-years at-risk of that event for all subjects at risk.
 
- Although the categorization of study follow-up time to Benlysta (Exposed) or Non-Benlysta (Unexposed) depends on the exposure assignment strategy (see Appendix 2, Section 9.2.1 for further discussion), the follow-up time included in the subject-years at-risk calculation, for each month xx time period, starts from enrollment date and ends at the earliest of the following: 
 
o First event date
 
o Last contact date (as defined in Section 9.5.3)
 
o Month xx target date (Section 5.3)
 
o Censored date (for While on Initial Exposure strategy; see Section 9.2.1.1)
 
o Data cut-off date
 
 
Additionally, for some exposure strategies (e.g. 'As-Exposed' strategy; see Appendix 2, Section 9.2.1.2), time to treatment switch and risk windows are also considered when categorizing follow-up time into 'Exposed' and 'Unexposed' period.
 
 
- Calculation of an individual's subject-years at-risk for each exposure strategy is shown in Section 9.2.
 
- Subject-years at-risk will be calculated for each event type separately.
 
- Only the first experience of the event (i.e. new cases) or first primary diagnosis (in the case of a malignant event) which occurred during the 'at-risk' period are counted (see Section 9.2.1 for time period considered for each exposure strategy).
 
- For summary of each specific AESI category, subjects experiencing events in multiple AESI categories will be counted in more than 1 AESI category.
 
 
2. Event rate will be computed for each exposure group as follows:
 $\text{Event rate} = \frac{\sum \text{all AESI events}}{\sum \text{subject years of follow-up}} \times 100$ 
 
- Event rate is estimated for potentially recurrent events and represents the average number of events per unit time of follow-up. It is defined as the total number of events experienced by all subjects during the specified study period divided by subject-years of follow-up. The categorization of study follow-up time depends on the exposure strategy (see Appendix 2, Section 9.2.1). The subject-years of follow-up for each month xx time period takes the same definition above for the subject-years at-risk, however, follow-up does not stop at the time of first event.
 
- Additionally, for some exposure strategies (e.g. 'As-Exposed' strategy), time to treatment switch and risk windows are also considered when categorizing follow-up time into exposed and unexposed period (Section 9.2.1.2)
 
- All events experienced during the follow-up period including recurrent events are counted (see Section 9.2.1 for time period considered for each exposure strategy).
 

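### SAP 9.3.2 allots each adverse event to one AESI category, which conflicts with SAP 9.3.1 and with the protocol's definition of serious infection, under which serious opportunistic infections are included

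*SAP*

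**What the plan says.** **Protocol, section 4.** The serious-infection outcome opens: "Serious infections, including serious opportunistic infections, are defined as those that result in death". Further criteria follow, including treatment with intravenous antimicrobials, and the section says that all serious infections are collected. Opportunistic infections and other infections of interest are collected whether serious or not. The categories therefore overlap by design.

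**SAP 9.3.1.** The automated step creates flags and adjudication variables for "assigning each AE to at least a specific AESI category".

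**SAP 9.3.2.** The medical review covers all reported AE terms. "The reviewers will categorize each AE into one of the following AESI category"; the six entries include opportunistic infections, other infections of interest and serious infections. Mortality has its own rule, based on fatal SAEs. For the rest, "All other AESI types are assigned based on the review outcome described above", and "The reconciled record of categorization will be utilized in study reporting". The section also says that "the eCRF field for reporting SAE will be used to separate serious and non-serious Opportunistic Infections and Other Infections of Interest AESI".

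**SAP 7.1.5.1.** For the category summaries, "subjects experiencing events in multiple AESI categories will be counted in more than 1 AESI category".

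**The concern.** A serious opportunistic infection meets two of the six entries in SAP 9.3.2, and so does a serious case of zoster, tuberculosis or Salmonella sepsis from the second part of protocol Appendix 1. If a reviewer must choose one entry and chooses the specific one, the event is not in the serious-infection category. Because the reconciled review determines the reported AESI type, the event would then be missing from the serious-infection numerator.

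Serious infection is a primary endpoint and has the highest planning rate in protocol Table 8-1. Its reported rate would describe a narrower endpoint than the protocol defines, and the SAP would not have declared the change. The comparison between cohorts would also be affected if the excluded infections were more frequent in one cohort than in the other.

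**Working it through.** **1. The texts, applied to one serious opportunistic infection**

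| Source | Consequence |
|---|---|
| Protocol section 4 | Counts as an opportunistic infection and as a serious infection |
| SAP 9.3.1 | May carry more than one category, but none of the twelve listed queries is a serious-infection query |
| SAP 9.3.2, category rule | Goes into one entry; read literally, not both |
| SAP 9.3.2, SAE field | Split into serious or non-serious within its own category; nothing adds the serious ones to serious infections |
| SAP 7.1.5.1 | A subject with events in several categories counts in each; silent on one event that meets two |
| SAP 2.1.1 | The only listed modification is separate rates for opportunistic and other infections of interest; no narrowing of serious infections |

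SAP 9.3.2 thus conflicts with 9.3.1 and with the protocol, and no other section resolves the conflict. Mortality shows that the authors wrote a separate overlap rule where they wanted one.

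**2. The plan's own figures (protocol section 8.2 and Table 8-1)**

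Inputs: 2,000 and 1,000 patients, 10% annual drop-out, 5 years; serious infection 5.80 and opportunistic infection 0.136 per 100 patient-years.

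- Patient-years = N × (1 − 0.9⁵)/(−ln 0.9) = 7,773.5 and 3,886.8 (stated: 7,773 and 3,886).
- Half-width of the 95% CI for a rate difference = 1.96 × √[rate × (1/7,773 + 1/3,886)].
- Serious infection: 1.96 × √[0.0580 × (1/7,773 + 1/3,886)] = 0.927 per 100 patient-years (stated: 0.93).
- Opportunistic infection: 0.142 (stated: 0.14).

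The stated figures are reproduced.

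**3. Loss from opportunistic infections under the literal rule**

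Assume that every opportunistic infection is serious and that all were counted in the 5.80. The documents confirm neither.

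- Share: 0.136/5.80 = 2.3%.
- Remaining rate: 5.80 − 0.136 = 5.664; half-width 0.916.
- Expected events lost: 0.136 × 77.73 = 10.6 and 0.136 × 38.86 = 5.3, out of 5.80 × 77.73 = 450.8 and 5.80 × 38.86 = 225.4.
- If half were serious: 0.068/5.80 = 1.2%, leaving 5.732.

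These are upper figures for the incidence rate as well. It counts only each subject's first event, so a subject with another serious infection later still counts.

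**4. Loss from other infections of interest**

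The documents give no rate for serious cases. Assumed rates of 0.25, 0.5 and 1.0 per 100 patient-years, added to 0.136, would give losses of 6.7%, 11.0% and 19.6% of 5.80. This shows only how strongly the answer depends on the missing input. Nothing in the documents favours any of these values.

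**5. Effect on the difference between cohorts**

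Equal absolute losses cancel. As an extreme, a loss of 0.136 in one cohort and none in the other would shift the difference by 0.136, which is 0.136/0.927 = 15% of the planned half-width.

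**The case against.** The best defence is that exclusivity is inferred. SAP 9.3.2 never says *only one* and describes the review as a way to flag AESIs. SAP 9.3.1 presents the manual review as the route for events that the automated step cannot place, and it allows several categories. SAP 2.1.1 says that the planned approach is unchanged, so the protocol definition should still govern. The SAP also cites a work instruction on AESI categorization that may already permit double flags. Finally, the events would not vanish: opportunistic and other infections of interest are primary endpoints of their own and can be split by seriousness.

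Much of this stands, and it rules out several stronger readings:

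- A reader might infer that these infections will certainly be dropped. The documents show a conflict and a literal rule, not what reviewers do in practice.
- A reader might infer that the protocol names other infections of interest as part of serious infections. It names only serious opportunistic infections; the others come in through the general definition.
- A reader might set an assumed loss in the serious-infection rate against the ±0.93. That figure is the half-width for a difference between cohorts, so only a differential loss can be compared with it.
- A reader might infer bias in favour of BENLYSTA from protocol Table 1-1, where opportunistic infections numbered 0, 1 and 2 on placebo, 1 mg/kg and 10 mg/kg. Three events establish no pattern, and the table does not say whether they were serious.

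The defence does not remove the conflict. SAP 9.3.2 covers all AE terms, not only those left over from the automated step, and its outcome is the one reported. A rule that may exist in a separate instruction does not correct the SAP's own text.

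**Conclusion.** The point holds as a conflict of definitions that should be resolved before database lock. Read literally, SAP 9.3.2 leaves serious opportunistic infections and serious other infections of interest out of the serious-infection endpoint, contrary to protocol section 4 and at odds with SAP 9.3.1.

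The part that can be sized is small: at most about 2.3% of the serious-infection rate, under the two assumptions in the working. The part due to other infections of interest is unknown, so the total cannot be called either negligible or large. No differential loss between cohorts has been shown. The case for correction is that a primary endpoint should match its protocol definition, not that a material bias has been demonstrated.

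**What to change.** In SAP 9.3.2, replace *one of* with *all applicable*, and align the sentence with 9.3.1 so that both sections say that an event may hold more than one category. Add that every opportunistic or other infection of interest meeting the protocol section 4 definition of a serious infection is also flagged as a serious infection, and derive that flag before database lock.

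The flag should rest on section 4 and not on the eCRF SAE field alone. Section 4 counts infections that need intravenous antimicrobials as serious. The list in protocol section 7.1, which section 7.4 tells investigators to use when judging seriousness, omits that criterion. Apply it where the data allow, and state in the SAP if they do not.

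The cost is a short text change and one derived flag. If reviewers already assign both categories, nothing else changes. If intravenous treatment has to be checked for infections recorded as non-serious, a limited look at those records is needed.

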## 9.4. Appendix 4: Data Display Standards & Handling Conventions

### 9.4.1. Reporting Process

Software	

 
All analyses will be conducted using SAS® version 9.4 or higher (SAS Institute, Cary, NC, USA).
 
	
Reporting Area:	

 
Datasets and TLF outputs received from FSO will be uploaded to
 
	
Domino Project	16267_116543_EOS
Compound/Study	GSK1550188\BEL116543
Analysis Datasets	

 
Analysis datasets will be created according to CDISC standards (SDTM IG Version 3.2 & Analysis Data Model (ADaM) IG Version 1.1).
 
	
Generation of RTF Files	

 
RTF files will be generated for each Table, Listing and Figure.
 
	

### 9.4.2. Reporting Standards

General

The current GSK Statistical Display Principles will be applied for reporting, unless otherwise stated.   GSK Statistical Display Principles location:  https://myteams.gsk.com/sites/IDSLLibrary/PublishingImages/Combined%20Statistical%20Displays%20Principles%20v2.docx ).
 
Below sections from “Combined Statistical Displays Principles v2.docx” will be applied:
 
 
4.3 to 4.24: Principles for All Displays
 
5.1 to 5.9: Principles for Data Listings
 
6.1 to 6.11: Principles for Summary Table
 
7.1 to 7.13: Principles for Graphics
 

Formats

 
GSK Statistical Displays Principles (4.24, 6.8.3, & 6.9) for decimal places (DP's) will be adopted for reporting of data based on the raw data collected, unless otherwise stated.
 
Numeric data will be reported at the precision collected on the eCRF.
 
The reported precision from non eCRF sources will follow the GSK statistical displays principles but may be adjusted to a clinically interpretable number of DP's.
 

Planned and Actual Time

 
Reporting for Tables, Figures and formal statistical analyses: 
 
Target visit dates will be used for slotting events. The analysis visit dates will be used for any displays with time point analysis and derivations.
 
 
 
Reporting for Data Listings: 
 
Unless otherwise stated, planned/scheduled time relative to study assessment will be shown for TLF (Refer to Statistical Displays Principle 5.5).
 
 
 

Unscheduled Visits

 
No unscheduled visit in the study
 

## 9.5. Appendix 5: Derived and Transformed Data

### 9.5.1. General

Multiple Measurements at One Analysis Time Point

 
All AESIs, SLE medications or hospitalizations reported since the last visit will be reported and analysed.
 
If there are multiple values available within a visit window, then the worst case will be used for analysis. If the worst-case values are equal, the visit with the earliest date will be selected. For laboratory, the measurement which takes place first will be selected as the value.
 
For SLICC and SLEDAI 2000, the worst-case value will be that which increases the total score.
 

### 9.5.2. Study and Concomitant Medication Phases

Study Phase	Definition
Historical	Date < Enrollment Date
Baseline	Enrollment Date
Follow-up	Date > Enrollment Date

Medication Phase	Definition	
Historical	Medications stopped prior to enrollment date (Day 1). For BENLYSTA only:  With regards to interruptions (i.e. stopping & restarting the medication), medications that stop within the 98 days window before enrollment, and don't restart within 98 days of the medication end date, will be classified as historical.	Medication End Date < Study Enrollment Date, excluding interruptions in medications for BENLYSTA only (as defined in the baseline medication phase)
Baseline	Medications started on or prior to enrollment date (Day 1) and still ongoing at or after enrollment, or for BENLYSTA only: Benlysta that stops within 98 days before enrollment and restarts, such that restart date – stop date ≤98 days and subsequent Benlysta end date is ongoing or after enrollment date. Such cases are considered interruptions, the medication is classified as baseline.	Medication Start Date ≤ Enrollment Date* ≤ Medication End Date, or accounting for interruptions for BENLYSTA only: Enrollment Date -98 ≤ Medication(A) End Date < Enrollment Date* and Subsequent Medication(B) Start Date ≤ Medication(A) End Date + 98 and ((Subsequent Medication(B) End date ≥ Enrollment Date) or (Subsequent Medication(B) End Date is missing))
Post-Baseline	Medication is still ongoing after enrollment day or medications end date is after enrollment.	Medication End Date is missing or Medication End Date > Enrollment Date

\* Consider SLE medication(s) started within 3 days following the enrollment date (i.e Medication started or initiated at Day 1, 2, 3, or 4) as Baseline Medication (i.e Enrollment Date ≤ Medication Start Date ≤ Enrollment Date +3)

Study Day

 
Calculated as the number of days from Enrollment Date (Day 1):                             
 
Ref Date = Missing → Study Day = Missing
 
Ref Date < Enrollment Date → Study Day = Ref Date – Enrollment Date
 
Ref Date ≥ Enrollment Date → Study Day = Ref Date – (Enrollment Date) + 1
 
 
 

For all parameters, changes from baseline will be derived as follows:

Definition	Reporting Details
Change from Baseline	= FU Visit Value – Baseline Value
% Change from Baseline	= 100 x [(FU Visit Value – Baseline Value) / Baseline Value]

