5.2 Exclusion Criteria

Patients will be excluded from participating in the registry if they meet any of the following exclusion criteria:

1. Treatment with an investigational drug within one year of enrollment. Investigational drug applies to any drug not approved for sale in the country it is being used.
2. Currently enrolled in a placebo-controlled BENLYSTA (belimumab) clinical trial or a continuation protocol where belimumab is used as an investigational agent.
3. Patients who have a history of BENLYSTA exposure, but are not currently receiving BENLYSTA.
4. Patients only receiving an anti-malarial for SLE.
5. Patients only receiving steroids for SLE.

6 Data Collection

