##### **First step of analysis: Inverse probability of treatment weighting (IPTW)**

Propensity scores will be computed as the probability of being exposed to Benlysta at enrollment given an individual’s baseline characteristics. Logistic regression will be used to derive the PS. Non-stabilized weights (i.e. IPTW) for each individual will be calculated as the inverse of the probability of receiving the actual exposure:  $1/PS$  for the Benlysta arm and  $1/(1-PS)$  for the Non-Benlysta arm.

Inverse probability of treatment weighting (IPTW) (Rosenbaum, 1983) will be used to adjust for differences in covariates balance between exposure groups, Benlysta versus Non-Benlysta. To reduce likelihood of extreme weights being assigned in the analysis, stabilized weights will be computed by multiplying the non-stabilized weight of each individual by the proportion of subjects who were exposed to Benlysta at enrollment :  $p/PS$  for the Benlysta arm and  $(1-p)/(1-PS)$  for the Non-Benlysta arm., (Chesnaye, 2021). For the remainder of the document, references to “weight” refer to stabilized weights.

These weights will create a *pseudopopulation* whereby confounding factors are balanced among Benlysta and non-Benlysta arms. The weights’ distributions will be checked to identify extreme weights which might impact results (see section 7.3.1.3). If the balance assessment reveals that adequate balance cannot be achieved between the Benlysta and non-Benlysta arms (section 7.3.1.2.2), no further analysis using propensity scores will be conducted.

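### A BENLYSTA restart up to 97 days after enrollment can decide the baseline exposure group, so part of the BENLYSTA person-time is death-free by construction

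*SAP*

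**What the plan says.** SAP 9.5.2 has an interruption rule for BENLYSTA only. It covers "Benlysta that stops within 98 days before enrollment and restarts": such a record is still a baseline medication if "restart date – stop date ≤98 days and subsequent Benlysta end date is ongoing or after enrollment date". In formula form the stop must satisfy "Enrollment Date -98 ≤ Medication(A) End Date < Enrollment Date" and the restart "Subsequent Medication(B) Start Date ≤ Medication(A) End Date + 98". Neither form places the restart on or before enrollment. In the historical row of the same table, records that stop in the same window and don't "restart within 98 days of the medication end date, will be classified as historical".

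This is more than a display rule. SAP 4.1 note [1] refers to 9.5.2 to decide who is BENLYSTA at enrollment, and assigns subjects on other immunosuppressants to NON-BENLYSTA. At-risk time starts at the enrollment date (SAP 7.1.5.1 and 9.2.1.1). As-Exposed period 1 takes the baseline group (9.2.1.2), and Ever-Exposed starts baseline BENLYSTA users at enrollment (9.2.1.3). The weighted analysis uses the same status: "Propensity scores will be computed as the probability of being exposed to Benlysta at enrollment" (SAP 7.3.1). Other SLE medications have a look-ahead of only three days (Day 1 to 4 rule, SAP 5.2 and 9.5.2).

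Protocol 5.2, exclusion 3, bars "Patients who have a history of BENLYSTA exposure, but are not currently receiving BENLYSTA".

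**The concern.** Take two patients with the same stop date before enrollment. The one who later restarts is BENLYSTA from Day 1. The one who does not, perhaps because of death, is not. Group membership at Day 1 thus uses information from after Day 1, while the clock runs from Day 1. For the patient classified by a later restart, the interval from enrollment to restart cannot contain a death. It still enters the BENLYSTA denominator, which is immortal time.

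Mortality is one of the primary endpoints of this safety registry, and the error lowers the BENLYSTA rate. No section requires the restart to precede enrollment, moves the start of follow-up, reports the number affected or plans a sensitivity analysis for these patients.

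**Working it through.** **Inputs.** Interruption rule: SAP 9.5.2. Cohort sizes of 2,000 and 1,000, 10% annual drop-out, 7,773 and 3,886 patient-years (PY), and mortality of 0.68 per 100 PY in both groups: protocol 8.2. Half-width of ±0.32: protocol Table 8-1. The share of patients affected is not given, so it is assumed.

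**The plan's own figures.** PY = N × (1 − 0.9^5)/(−ln 0.9) = N × 3.88675. This gives 7,773.5 for 2,000 and 3,886.8 for 1,000, in agreement with the protocol. The half-width is 1.96 × sqrt(0.0068 × (1/7,773 + 1/3,886)) × 100 = 0.318 per 100 PY, which matches the ±0.32 in Table 8-1 (the running text of 8.2 prints ±0.30).

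**Length of the look-ahead.** Write E for the enrollment date. A stop at E−k, with k from 1 to 98, allows a restart up to E−k+98.
- k = 1: latest restart E+97 (Study Day 98).
- k = 95: latest restart E+3, already covered by the Day 1 to 4 rule.
- k = 98: latest restart E.

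So stops from E−94 to E−1 can be classified by a restart between E+4 and E+97. If the asterisk on the enrollment date in the formula is read as E+3, the limit becomes E+100.

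**Size.** Death-free PY = 2,000 × share × 97/365.25, with every affected patient at the maximum. Expected deaths in that time, d, are PY × 0.0068, against 7,773 × 0.0068 = 52.9 in the whole BENLYSTA cohort. The last column is the larger case, in which deaths before restart leave BENLYSTA and are counted in NON-BENLYSTA: 100 × (d/7,773 + d/3,886).

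| Assumed share | Patients | Death-free PY | % of 7,773 | d | Shift in rate difference, per 100 PY |
|---|---|---|---|---|---|
| 1% | 20 | 5.3 | 0.07% | 0.04 | 0.0014 |
| 5% | 100 | 26.6 | 0.34% | 0.18 | 0.0070 |
| 10% | 200 | 53.1 | 0.68% | 0.36 | 0.0139 |

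In the 10% row, a true mortality ratio of 1.00 becomes (52.86 − 0.36)/52.86 = 0.993 if patients who die before restart are excluded, or 0.980 if they are counted as NON-BENLYSTA.

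**A less extreme gap.** If stop date and gap length are both uniform (assumption), restarts after E+3 fall on average at E+35. Then 1% gives 2,000 × 0.01 × 35/365.25 = 1.9 PY (0.02%) and 5% gives 9.6 PY (0.12%).

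**First 12 months.** SAP 7.1.5.1 also provides for rates by time period. Person-time in year 1 is 2,000 × 0.1/(−ln 0.9) = 1,898 PY, so at the 97-day maximum the death-free share is 5.3/1,898 = 0.28% at 1% and 26.6/1,898 = 1.40% at 5%.

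**The case against.** The rule has a sound purpose. It mirrors the switching definition in SAP 5.1, where a BENLYSTA gap of up to 98 days is an interruption and not a switch. It also covers stop-restart pairs that both precede enrollment, and it would catch formulation changes, for which protocol 6.2 closes one record and opens another. Sites verify eligibility at enrollment (protocol 6.1), so patients who have truly stopped should already be screened out. All of this stands for restarts on or before enrollment, and calling the gap exposed time fits the 14-week window. It does not answer the fault, which is that the status goes only to those who later restart.

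Three stronger readings are tempting, and the documents do not support them.
- A reader might infer that the rule favours BENLYSTA on every AESI. It guarantees only survival and continued follow-up. A serious infection in the gap of a patient who then restarts is counted for BENLYSTA. Six of the seven endpoints in SAP 2.2 can occur non-fatally in the gap.
- A reader might infer that non-restarters simply drop out under exclusion 3. SAP 4.1 note [1] would instead make those on an immunosuppressant NON-BENLYSTA.
- A reader might infer that the propensity model as a whole is built on post-enrollment exposure. That is true only for this subset, whose size is unknown.

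One obvious remedy also fails: counting every stop within 98 days before enrollment as BENLYSTA, restart or not. It conflicts with exclusion 3. It also upsets While On Initial Exposure, where the switch date is the BENLYSTA end date plus 98 days and events count up to the day before. A stop at E−98 then leaves no event window, and a stop at E−90 leaves 8 days.

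**Conclusion.** The point holds for mortality. SAP 9.5.2 lets a restart as late as Enrollment+97 set the baseline group while the clock starts at enrollment, so BENLYSTA mortality is biased downward. For non-fatal AESI the direction cannot be established from the documents.

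The effect is probably small. Even at an assumed 10% share and the maximum gap, the mortality rate difference moves by at most about 0.014 per 100 PY, against a half-width of 0.32. The analyses are descriptive, without hypothesis tests (SAP 2.4), so a changed conclusion is unlikely. These figures rest on the assumed shares and gaps and on the planning mortality rate applying in the gap. The case for acting is that the plan conditions on the future in a primary endpoint and the repair is cheap. Separately, the fate of non-restarters is unresolved between the two documents, and counting them as NON-BENLYSTA makes the bias larger.

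**What to change.** 1. Keep the interruption rule when the restart falls on or before enrollment, or within the existing Day 1 to 4 rule.
2. When the restart is later, start that patient's at-risk and follow-up time at the restart date in all exposure strategies.
3. Report how many patients are affected, and repeat Tables 24.110, 24.120, 54.010 and 54.020 without them.
4. Reconcile protocol exclusion 3 with SAP 4.1 note [1]: state whether non-restarters taking an immunosuppressant are excluded or counted as NON-BENLYSTA.

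The cost is one change to the start-date derivation and four repeated tables. A few person-years are lost and a few patients have a later start date. Any non-fatal AESI in the dropped interval leaves the rates, so these events should be listed.
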